## 2. STUDY SYNOPSIS

Study Title:	MIMICS-2: Evaluation of Safety and Effectiveness of the BioMimics 3D™ Stent System in the Femoropopliteal Arteries of Patients with Symptomatic Peripheral Arterial Disease										
Study Objective:	To demonstrate that the BioMimics 3D Stent System meets the performance goals defined by VIVA Physicians, Inc. for the safety and effectiveness of Nitinol stents used in the treatment of symptomatic disease of the femoropopliteal artery.										
Study Device:	BioMimics 3D™ Stent System										
Intended Use:	The BioMimics 3D stent is intended to improve luminal diameter in the treatment of symptomatic de-novo, obstructive or occlusive lesions in native femoropopliteal arteries with reference vessel diameters ranging from 4.0 – 6.0 mm										
Study Design:	Prospective, single-arm, multicenter clinical trial										
Device Regulatory Status:	
United States Class III investigational device
 
Europe CE Mark approval (Class IIb)
 
Japan Class III investigational device
 
BioMimics 3D Stent System has been designed and is manufactured by Veryan Medical Limited under the control of Veryan's Quality Management System. Veryan is ISO 13485 certified.
										
Estimated Enrollment:	
280 subjects. Up to 40% (112 subjects) of total study population may be enrolled outside the United States
 
No site may enroll more than 35 subjects.
										
Subject Population:	Subjects with symptomatic atherosclerotic disease of the femoropopliteal artery who comply with all study eligibility criteria.										
Clinical Sites:	Up to 40 centers in the United States. Up to 13 centers in Japan and Europe.										
Study Follow-Up:	After the index procedure on Day 0, subjects will be evaluated within 30 days, then at Months 12, 24 and 36.										
Study Duration:	
 
 First subject enrolled:	June, 2015	
 
 Last subject enrolled:	October, 2016	
 
 Last subject completes Month 12 Visit:	December, 2017	
 
 Last subject completes Month 24 Visit:	December, 2018	
 
 Long-term surveillance completed (Month 36):	December, 2019	
 
	First subject enrolled:	June, 2015	Last subject enrolled:	October, 2016	Last subject completes Month 12 Visit:	December, 2017	Last subject completes Month 24 Visit:	December, 2018	Long-term surveillance completed (Month 36):	December, 2019
First subject enrolled:	June, 2015										
Last subject enrolled:	October, 2016										
Last subject completes Month 12 Visit:	December, 2017										
Last subject completes Month 24 Visit:	December, 2018										
Long-term surveillance completed (Month 36):	December, 2019										

Primary Outcome Measures:
	
Primary safety endpoint: A composite of major adverse events (MAE) comprising death, any major amputation performed on the target limb or clinically-driven target lesion revascularization (TLR) through 30 days.
 
Primary effectiveness endpoint: Primary stent patency rate at 12 months. Patency is defined as no significant reduction in luminal diameter (i.e. < 50% diameter stenosis) since the index procedure. Luminal diameter is assessed by core lab using angiography or duplex ultrasound imaging. Loss of primary stent patency is deemed when peak systolic velocity ratio (PSVR) is >2.0, or where angiography reveals >50% diameter stenosis, or where the subject undergoes clinically-driven TLR. When both imaging modalities are available, angiography takes precedence.
 


Secondary Outcome Measures:
	
 
1. Contribution of individual MAE rates for death, major amputation performed on the target limb and clinically-driven target lesion revascularization to the overall MAE rate at 30 days.
 
2. Long-term safety assessment – overall MAE rate at Month 12 and contribution of individual event rates to the overall MAE.
 
3. Overall rate and incidence of type of serious adverse events from Day 0 through completion of Study follow-up at Month 36.
 
4. Technical success reported by the core lab as the percentage of treated lesions in which a final result of ≤50% residual diameter stenosis (in-stent) was achieved at index procedure.
 
5. Primary stent patency rate: determined at Months-12 and 24 using values of: PSVR >2.0; >2.4; >2.5; and >3.5, each to indicate loss of patency on duplex ultrasound or where angiography reveals >50% diameter stenosis or where the subject
 

	
undergoes clinically-driven TLR. When both imaging modalities are available, angiography takes precedence.
 
 
6. Clinical outcome: comparison of Rutherford Clinical Category measured at Baseline, Day 30, Months 12 and 24. Worsening of Rutherford Clinical Category is defined as an increase by one or more categories compared to Baseline or unexpected major amputation of the target limb.
 
7. Clinical outcome: comparison of Six-Minute Walk Test measured at Baseline, Day 30, Months 12 and 24 (subgroup of US investigational sites only).
 
8. Functional outcome: comparison of the ankle brachial index (ABI) measurement at Baseline, within 30 days after index procedure, then at Months 12 and 24.
 
9. Functional outcome: comparison of the Walking Impairment Questionnaire at Baseline, within 30 days after index procedure, then at Months 12 and 24.
 
10. Stent integrity measured as freedom from stent fracture, defined as clear interruption of a stent strut observed in a minimum of two projections, determined by core lab examination of X-rays taken with the leg in extension at 12, 24 and 36 Months.
 

[REDACTED]
	
[REDACTED]


Inclusion Criteria:
	
 
1. Subject is male or female, with age >18 and ≤85 years at date of enrollment.
 
2. Subject or authorized representative provides written informed consent before any study-specific investigations or procedures.
 
3. Subject is willing to undergo all follow-up assessments according to the specified schedule over 36 months.
 
4. Subject is a suitable candidate for angiography and endovascular intervention and, if required, is eligible for standard surgical repair.
 
5. Subject has symptomatic peripheral arterial disease (PAD) of the lower extremities requiring intervention to relieve de novo obstruction or occlusion of the native femoropopliteal artery.
 
6. Subject has PAD classified as Rutherford clinical category 2, 3 or 4.
 
7. Subject has documented PAD by either (i) a resting ankle-brachial index (ABI) of ≤0.90 (or ≤0.75 after exercise of the target limb). Resting toe brachial index (TBI) is performed only if unable to reliably assess ABI. TBI must be <0.70; or (ii)
 

[REDACTED]

	Normal ABI with angiographic or ultrasound evidence of $\geq 60\%$ diameter stenosis.
Angiographic Inclusion Criteria:	
 
8. Subject has single or multiple stenotic or occlusive lesions within the native femoropopliteal artery (“target lesions”) that can be crossed with a guidewire and fully dilated. (Note: multiple target lesions must be treated as a single lesion.)
 
9. Single or multiple target lesions must be covered by a single stent or two overlapping stents. In the case of tandem lesions, the gap between lesions must be <math>\leq 3</math> cm.
 
10. Target lesion(s) eligible for treatment under the Protocol are at least 1 cm distal to the origin of the deep femoral artery and at least 3 cm above the bottom of the femur.
 
11. Target lesion(s) reference vessel diameter is between 4.0 mm and 6.0 mm by operator’s visual estimate.
 
12. Single or multiple target lesions measure <math>\geq 40</math> mm to <math>\leq 140</math> mm in overall length, with <math>\geq 60\%</math> diameter stenosis by operator’s visual estimate.
 
13. Subject has a patent popliteal artery (no stenosis <math>\geq 50\%</math>) distal to the treated segment.
 
14. Subject has at least one patent infrapopliteal vessel (<math>< 50\%</math> stenosis) with run-off to the ankle.
 

Exclusion Criteria:	
 
1. Subject is unable or is unwilling to comply with the procedural requirements of the study Protocol or will have difficulty in complying with the requirements for attending follow-up visits.
 
2. Subject has a comorbidity that in the investigator’s opinion would limit life expectancy to less than 36 months.
 
3. Subject has iliac stent in target limb that has required re-intervention within 12 months prior to index.
 
4. Subject has any planned major surgical procedure (including any amputation of the target limb) within 30 days after the index procedure for this Study.
 
5. Subject has a target vessel that has been treated with any type of surgical or endovascular procedure prior to enrollment.
 
6. Subject has a target vessel that has been treated with bypass surgery.
 
7. Subject has PAD classified as Rutherford clinical category 0, 1, 5 or 6.
 
8. Subject has known or suspected active systemic infection at the time of enrollment.
 
9. Subject has a known coagulopathy or has bleeding diatheses, thrombocytopenia with platelet count less than 100,000/microliter or INR <math>> 1.8</math>.
 
10. Subject has a stroke diagnosis within 3 months prior to enrollment.
 

	
 
11. Subject has a history of unstable angina or myocardial infarction within 60 days prior to enrollment.
 
12. Subject has a contraindication to antiplatelet, anticoagulant, or thrombolytic therapies.
 
13. Subject has known allergy to contrast agents or medications used to perform endovascular intervention that cannot be adequately pre-medicated.
 
14. Subject has known allergy to titanium, nickel or tantalum.
 
15. Subject has received thrombolysis within 72 hours prior to the index procedure.
 
16. Subject has acute or chronic renal disease (e.g., as measured by a serum creatinine of >2.5 mg/dL or >220 umol/L), or on peritoneal or hemodialysis.
 
17. Subject requiring coronary intervention within 7 days prior to enrollment.
 
18. Subject is pregnant or breast-feeding.
 
19. Subject is participating in another research study involving an investigational product (pharmaceutical, biologic, or medical device).
 
20. Subject has other medical, social or psychological problems that, in the opinion of the investigator, preclude them from receiving this treatment, and the procedures and evaluations pre- and post-treatment.
 

Angiographic Exclusion Criteria:
	
 
21. Subject has significant disease or obstruction (<math>\geq 50\%</math>) of the inflow tract that has not been successfully treated at the time of the index procedure (success measured as <math>\leq 30\%</math> residual stenosis, without complication).
 
22. Subject has a lesion in the contralateral limb requiring intervention during index procedure or within next 30 days.
 
23. Subject has no patent (<math>\geq 50\%</math> stenosis) outflow vessel providing run-off to the ankle.
 
24. There is a lack of full expansion in the predilatation balloon.
 
25. Target lesion(s) requires percutaneous interventional treatment, beyond standard balloon angioplasty alone, prior to placement of the study stent.
 
26. Evidence of aneurysm or acute thrombus in target vessel.
 

[REDACTED]
	
[REDACTED]

[REDACTED]	[REDACTED]

### 3. LIST OF ABBREVIATIONS AND DEFINITIONS OF TERMS

Abbreviation	Definition
6MWT	Six-Minute Walk Test
ABI	Ankle Brachial Index
AE	Adverse Event
CDTLR	Clinically Driven Target Lesion Revascularization
CEC	Clinical Events Committee
CFR	Code of Federal Regulation
eCRF	electronic Case Report Form
EC	Executive Committee
GCP	Good Clinical Practice
ICH	International Conference on Harmonisation
ITT	Intent to Treat
IQR	Interquartile Range
IRB	Institutional Review Board
MAE	Major Adverse Event
mITT	modified Intent to Treat
NYHA	New York Heart Association
OPG	Objective Performance Goal
OUS	Outside United States
PAD	Peripheral Artery Disease
PMA	Premarket Approval
PTA	Percutaneous transluminal angioplasty
PSVR	Peak Systolic Velocity Ratio
PVD	Peripheral Vascular Disease
RVD	Reference Vessel Diameter
RCC	Rutherford Clinical Category
SAE	Serious Adverse Event
SAS	Statistical Analysis System
TBI	Toe Brachial Index
TLR	Target Lesion Revascularization
TVR	Target Vessel Revascularization
US	United States
VIVA	Vascular Interventional Advances
WIQ	Walking Impairment Questionnaire

**Abbreviation**  
6MWT

**Definition**  
Six-Minute Walk Test

## 4. INTRODUCTION

The purpose of this statistical analysis plan is to provide additional details on the derivation of variables and statistical analyses to be performed for this study. The database will lock when the 12-month visit is completed for all patients. All planned analyses will be performed at this time. There will continue to be annual follow-up visits for the collection of relevant medications and adverse events for 2 additional years. Interim analyses will be conducted for annual progress reporting as described herein.

## 5. STUDY OBJECTIVES

The objective of the study is to demonstrate that the BioMimics 3D Stent System meets the performance goals defined by VIVA Physicians, Inc. for the safety and effectiveness of Nitinol stents used in the treatment of symptomatic disease of the femoropopliteal artery.

## 6. INVESTIGATIONAL PLAN

### 6.1. Overall Study Design and Plan

The MIMICS-2 Study is a prospective, single arm, multicenter trial to demonstrate the safety and effectiveness of Veryan's BioMimics 3D Stent System. The BioMimics 3D self-expanding Nitinol stent is intended to improve luminal diameter in the treatment of symptomatic de-novo obstructive or occlusive lesions in native femoropopliteal arteries with reference vessel diameters ranging from 4.0 – 6.0 mm. Safety and effectiveness outcomes in the MIMICS-2 study will be compared to established performance goals defined by VIVA Physicians, Inc. for the clinical evaluation of safety and effectiveness of Nitinol stents used in the treatment of symptomatic disease of the femoropopliteal artery.

A total of 280 subjects will be enrolled into the MIMICS-2 Study to provide 230 subjects for evaluation at 12 months. This study will be conducted in up to 40 centers in the US and up to 13 centers in Europe and Japan. Up to 40% of total study population may be enrolled outside the US. A minimum of 30 evaluable subjects is required in Japan for the 12 month assessment time point. No site may enroll more than 35 subjects.

#### 6.1.1. Choice of Control Groups

There is no concurrent control group in this study. Primary effectiveness and safety will be compared to the performance goals defined by VIVA Physicians, Inc. for the clinical evaluation of safety and effectiveness of Nitinol stents used in the treatment of symptomatic disease of the femoropopliteal artery.

#### 6.1.2. Method of Assigning Patients to Treatment Groups

This is a single arm study.

### 6.2. Study Endpoints

#### 6.2.1. Primary Safety Endpoints

The primary outcome measure for safety in the MIMICS-2 Study is a composite of major adverse events (MAE) comprising death, any major amputation performed on the index limb or Clinically Driven Target Lesion Revascularization (CDTLR) through 30 days. The outcome will be

compared to the safety performance goal of 88% for bare Nitinol stenting as defined by VIVA Physicians.

### 6.2.2. Primary Effectiveness Endpoint

The primary outcome measure for effectiveness in the MIMICS-2 Study is primary stent patency rate at 12 months.

Patency is defined as no significant reduction in luminal diameter (i.e., < 50% diameter stenosis) since the index procedure. Luminal diameter is the value determined by the independent core lab. Loss of primary stent patency is deemed when PSVR >2.0, or where angiography reveals >50% diameter stenosis, or where the subject undergoes CDTLR. When both imaging modalities are available, angiography takes precedence.

[REDACTED]

### 6.2.3. Secondary Endpoints

1. Contribution of individual MAE rates for death, major amputation performed on the target limb and CDTLR to the overall MAE rate at 30 days.
2. Long-term safety assessment – overall MAE rate at Month 12 and contribution of individual event rates to the overall MAE.
3. Overall rate and incidence of type of serious adverse events from Day 0 through completion of Study follow-up at Month 36.
4. Technical success reported by the core lab as the percentage of treated lesions in which a final result of ≤50% residual diameter stenosis (in-stent) was achieved at index procedure.
5. Primary stent patency rate: determined at Months 12 and 24 using values of: PSVR >2.0; >2.4; >2.5; and >3.5, each to indicate loss of patency on duplex ultrasound or where angiography reveals >50% diameter stenosis or where the subject undergoes CDTLR. When both imaging modalities are available, angiography takes precedence.
6. Clinical outcome: comparison of Rutherford Clinical Category measured at Baseline, Day 30, Months 12 and 24. Worsening of Rutherford Clinical Category is defined as an increase by one or more categories compared to Baseline or unexpected major amputation of the target limb.

[REDACTED]

[REDACTED]

7. Clinical outcome: comparison of Six-Minute Walk Test measured at Baseline, Day 30, Months 12 and 24 (sub-group of investigational sites).
8. Functional outcome: comparison of the ankle brachial index (ABI) measurement at Baseline, within 30 days after index procedure, then at Months 12 and 24.
9. Functional outcome: comparison of the Walking Impairment Questionnaire at Baseline, within 30 days after index procedure, then at Months 12 and 24.
10. Stent integrity measured as freedom from stent fracture, defined as clear interruption of a stent strut observed in a minimum of two projections, determined by core lab examination of X-rays taken with the leg in extension at 12, 24 and 36 Months.

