## 8. PATIENT POPULATIONS

### 8.1. Analysis Populations

- *Intention-to-Treat (ITT) Analysis Set*: includes all enrolled subjects.
- *Modified Intention-to-Treat (mITT) Analysis Set*: includes all enrolled subjects in whom the BioMimics 3D Stent is implanted. Those subjects in whom the procedure is aborted without deployment (implantation) of a stent are excluded in this analysis set. This is the primary analysis set for the primary safety and effectiveness endpoints, as well as secondary and exploratory endpoints. If no subjects are excluded, that is, if the ITT and mITT analysis sets contain the same subjects, then all mITT analyses will revert to the ITT analysis set and the mITT analysis set will be eliminated.

- *Per Protocol (PP) Analysis Set*: includes all mITT subjects who additionally met all inclusion/exclusion criteria. This is a secondary analysis set for the primary safety and effectiveness endpoints, as well as secondary endpoints.

While mITT is intended as the primary analysis set for all safety and effectiveness endpoints, the primary safety and effectiveness endpoints will additionally be evaluated in the ITT and PP analysis sets as supportive information. All subjects excluded from mITT and PP analysis sets will be described in the final study report and the reasons detailed. If the ITT and mITT analysis sets contain the same subjects, then all mITT analyses will revert to the ITT analysis set and the mITT analysis set will be eliminated.

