### 9.3. Patient Disposition, Demographics and Other Baseline Characteristics

A tabulation of patient disposition will be presented including number enrolled, number treated, and number of withdrawals, including reasons for withdrawal as documented on the case report form.

The demographics and medical history will be presented in tabular form for all subjects enrolled in this study (ITT analysis set). Means, standard deviations, and sample size will be used to summarize continuous characteristics such as age. Percentages, raw number of subjects exhibiting a characteristic, and sample size will be used to summarize categorical characteristics such as gender. Demographic and medical history data will be additionally tabulated for the mITT and PP analysis sets.

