## 9.5. Secondary Endpoint Analyses

All secondary endpoints as described in Section 6.2.3 will be tabulated. Means, standard deviations and sample size will be used to summarize continuous characteristics. Distributions of continuous data will be examined and if non-normality is exhibited, medians and interquartile ranges will be presented. Percentages, raw number of subjects exhibiting a characteristic, and sample size will be used to summarize categorical characteristics. Measures collected serially over time (for example, ABI) will be presented at each time point, and the measure at each time point will be compared to the baseline measure as well as tested for trends. All available data will be used for each endpoint and no imputations will be done. The mITT analysis set will be used for these analyses.

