### 9.7.2. Device Failures, Malfunctions

The number of device failures and malfunctions will be tabulated and included in a listing.

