## 12. STATISTICAL TABLES TO BE GENERATED

### Disposition/Demographics/Procedure

Table 1.1	Subject Disposition
Table 1.2	Subject Enrollment by Site
Table 2.1	Baseline Demographics
Table 2.2	Relevant Medical History & Risk Factors
Table 2.3	Baseline Demographics by Country
Table 2.4	Relevant Medical History & Risk Factors - By Country
Table 3.	Site Reported Procedure Details
Table 4.1	Site Reported Target Lesion Summary - Lesion Preparation / Pre-Dilatation
Table 4.2	Site Reported Target Lesion Summary - Stent Delivery System & Stent Deployment Procedure
Table 4.3	Site Reported Target Lesion Summary - Post-Treatment / Post-Dilatation of Target Lesion
Table 4.4	Site Reported Non-Target Lesion Summary

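### Technical success is conditional on implantation: an attempted delivery that ends without a stent cannot count as a failure

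*SAP*

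**What the plan says.** Section 6.2.3, item 4, sets technical success as "the percentage of treated lesions in which a final result of ≤50% residual diameter stenosis (in-stent) was achieved at index procedure", reported by the core laboratory. The synopsis and section 9.5.1 repeat the definition.

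The analysis set comes from two places. Section 9.5 states for the secondary endpoints: "The mITT analysis set will be used for these analyses". Section 8.1 limits mITT to enrolled subjects who received the study stent and adds: "Those subjects in whom the procedure is aborted without deployment (implantation) of a stent are excluded in this analysis set". The per-protocol set, which section 8.1 names as the secondary set for secondary endpoints, "includes all mITT subjects who additionally met all inclusion/exclusion criteria". The ITT set "includes all enrolled subjects", but sections 8.1 and 9.4 plan it as a supportive analysis for the primary endpoints only.

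Several other outputs can show a procedure that ended without a stent:
- Section 9.3 tabulates "number enrolled, number treated, and number of withdrawals".
- Section 8.1 commits the final report to describing every subject excluded from mITT, with reasons.
- Section 9.7.2 says: "The number of device failures and malfunctions will be tabulated and included in a listing".
- Section 12 lists Table 4.2, on "Stent Delivery System & Stent Deployment Procedure", and Table 10, on device observations.

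**The concern.** Technical success is commonly read as how often the operator obtained the intended acute result with the device. Failure to place the stent is the plainest way for that to go wrong, and the SAP foresees it, because section 8.1 has a rule to remove such subjects.

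The exclusion acts twice. The criterion is an in-stent measurement, which cannot exist without a stent, and both analysis sets named for this endpoint require implantation. The rate is thus selected on part of the outcome that it appears to measure. If it is quoted alone, a reader may take a result among implanted lesions for a result among attempts. Because the rate is likely to be near 100%, a handful of failed deliveries could be most or all of the acute failures in the trial.

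**Working it through.** The SAP states no target, expected rate or sample size for technical success, so there is no figure of its own to reproduce. The check is of the definition, followed by denominator arithmetic.

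**Definition.** Take an enrolled subject in whom delivery was attempted and no stent was implanted.
1. Numerator: there is no in-stent residual stenosis to measure, so the lesion cannot be a success.
2. Denominator in mITT: section 8.1 removes the subject, so the lesion is not a failure either.
3. Denominator in per-protocol: this set is drawn from mITT, so the result is the same.
4. Reversion to ITT: section 8.1 allows this only when ITT and mITT contain the same subjects, so it never applies when such a subject exists.
5. Moving the endpoint to ITT: not enough by itself, because treated lesions and the in-stent criterion would still leave the case without a place in the rate.

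**Inputs.**
- N = 271 enrolled (section 9.1, final sample size determination).
- One lesion per subject, because the synopsis (angiographic inclusion criterion 8) requires multiple target lesions to be treated as a single lesion.
- k = failed deliveries. Not given; assumed to be 2, 5 or 8.
- f = implanted lesions that miss the 50% criterion. Not given; assumed to be 0, 3 or 6.
- Delivery is assumed to have been attempted in all 271.

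**Formulas.**
- Rate as defined (mITT): (N − k − f)/(N − k).
- Rate per attempted delivery: (N − k − f)/N.
- Gap: the mITT rate × k/N. With f = 0 this is k/N, and 1/271 = 0.37 points per failed delivery.

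**Results** (gaps taken before rounding).

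| f | k | Rate as defined | Per attempt | Gap (points) |
|---|---|---|---|---|
| 0 | 2 | 269/269 = 100% | 269/271 = 99.26% | 0.74 |
| 0 | 5 | 266/266 = 100% | 266/271 = 98.15% | 1.85 |
| 0 | 8 | 263/263 = 100% | 263/271 = 97.05% | 2.95 |
| 3 | 2 | 266/269 = 98.88% | 266/271 = 98.15% | 0.73 |
| 3 | 5 | 263/266 = 98.87% | 263/271 = 97.05% | 1.82 |
| 3 | 8 | 260/263 = 98.86% | 260/271 = 95.94% | 2.92 |
| 6 | 2 | 263/269 = 97.77% | 263/271 = 97.05% | 0.72 |
| 6 | 5 | 260/266 = 97.74% | 260/271 = 95.94% | 1.80 |
| 6 | 8 | 257/263 = 97.72% | 257/271 = 94.83% | 2.88 |

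In each block the rate as defined hardly moves as k rises from 2 to 8, while the rate per attempt falls by more than 2 points. With k = 0 the two rates coincide.

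**The case against.** The best case for the SAP has four parts.

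*The rate is stated openly and consistently.* All three places give the same denominator and the same in-stent criterion, and section 9.5 names the set. This stands: the rate is not miscalculated. It does not answer the point that the endpoint's name promises more than its denominator delivers.

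*Failed deliveries are reported elsewhere.* This also stands. A reader might infer that the plan hides them, and the documents do not support that. They can be seen in the disposition table, the description of mITT exclusions, the device failure listing and the deployment and device tables. What is lacking is a defined success rate that includes them; a reader would have to assemble it from several outputs.

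*Part of the text is blacked out.* There are redacted blocks beside the secondary endpoints, exploratory endpoints are mentioned but not visible, and the numbering passes from 9.5 to 9.7. A per-attempt measure may exist there, so it cannot be said that the plan has none. The point is therefore confined to how the visible endpoint is defined, which redacted text does not alter.

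*Nothing is decided on this endpoint.* It is descriptive, with no hypothesis or goal. This stands, and it limits the weight of the point.

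A reader might go further and infer that the same exclusion undermines the supportive ITT patency result. The documents do not support that as a separate defect. Section 9.2.3 and Figure 1a plan a tipping point analysis for patency in the ITT set, and counting subjects without a patency status as not patent is largely the adverse end of that analysis. The supportive ITT result has no role in the success decision.

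**Conclusion.** The point holds as a matter of definition and labelling. Technical success as written is conditional on implantation, and an attempted delivery that leaves no stent cannot count against it. It exceeds the rate per attempted delivery by about 0.37 points per failed delivery of 271, which is roughly 0.7, 1.8 or 2.9 points for 2, 5 or 8 failures, and zero if there were none.

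These sizes are illustrations. They rest on assumed failure counts, one lesion per subject, and an attempt in every enrolled subject. If some procedures were aborted before any delivery attempt, those subjects belong in neither numerator nor denominator and the gap is smaller for the same number of aborted procedures.

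The finding does not reach the primary analyses. Both primary endpoints remain in mITT under sections 9.4.1 and 9.4.2, and trial success is judged on them alone. Nor does the title of Listing 2, which refers to exclusions from an ITT set that contains every enrolled subject, add weight: it is a clerical slip.

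**What to change.** In section 6.2.3, and wherever the definition is repeated:
1. Keep the present rate and label it technical success among implanted lesions.
2. Add a second rate whose denominator is all enrolled subjects in whom delivery of the study stent was attempted, with non-deployment counted as failure. Write this denominator into the definition, since naming the ITT set alone would not bring these cases in.
3. List separately any procedure aborted before delivery was attempted, so that it is not counted as a device failure.

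As a clerical correction, retitle Listing 2 to refer to exclusions from mITT.

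The cost is a change of wording, one more table row and one listing title. The only data item needed is whether delivery was attempted. The drawback for the sponsor is a second figure that is equal to or slightly less favourable than the present one. The primary analyses and the mITT set need no change.
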